3. PARTICIPANT SELECTION

3.1 Eligibility Criteria

Participants must meet the following criteria on screening examination to be eligible to participate in the study:

- 3.1.1 Participants must have histologically or cytologically confirmed urothelial carcinoma of the bladder.
- 3.1.2 Participants must have cT2-T4N0 disease at the time of the study, as defined by conventional CT or MRI imaging. Patients must have no definite evidence of locoregional or distant metastatic disease at the time of study eligibility, as defined by conventional imaging.
- 3.1.3 Radical cystectomy must be planned for the patient after the planned ¹⁸F-fluciclovine-PET/CT.
- 3.1.4 Patients may or may not have had prior neoadjuvant therapy prior to this study.
- 3.1.5 Age ≥ 18 years. Since no dosing or adverse event data are currently available on the use of ¹⁸F-fluciclovine in participants <18 years of age, and the majority of bladder cancer occur in the adult population [42], children are excluded from this study but will be eligible for future pediatric trials.
- 3.1.6 ECOG performance status ≤ 2 (Karnofsky $\geq 60\%$, see Appendix A)
- 3.1.7 Ability and willingness to comply with the study procedures.
- 3.1.8 The effects of ¹⁸F-fluciclovine on the developing human fetus are unknown. For this reason and because radiopharmaceuticals may be teratogenic, women of childbearing potential and men must agree to use adequate contraception (barrier method of birth control; abstinence) prior to study entry and for 24 hours after the PET/CT scan is completed. Should a woman become pregnant or suspect she is pregnant while participating in this study, she should inform her treating physician immediately.
- 3.1.9 Ability to understand and the willingness to sign a written informed consent document

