5.3 Surgery

After completion of the ¹⁸F-fluciclovine-PET/CT scan, participants will undergo standard-of-care radical cystectomy surgery as determined by medical oncology and urology. If surgical plans (for example, the presence of unsuspected extensive disease precluding cystectomy) are altered based on clinical findings during surgery, the patient may remain evaluable if a lymph node dissection is performed as determined by the study team. Results from the standard-of-care evaluation of the pathologic specimens will be collected and reviewed. This includes evaluation of pathological samples for metastatic cancer burden.

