13.2 Data Analysis Plan

The primary and first secondary analyses will include all 16 eligible and treated patients with completed ¹⁸F-fluciclovine-PET/CT scans and pathology dissection. Among these 16 patients, those who undergo cystectomy will be included for secondary analysis 2 and 3.

We will tabulate the metastatic disease status by ¹⁸F-fluciclovine-PET/CT (limited to bladder, locoregional nodes positive, or distant) and pathologic stage at radical cystectomy and compute the agreement rate, along with the corresponding 90% exact binomial confidence interval (CI). The proportion of patients who show positive ¹⁸F-fluciclovine-PET/CT will be computed, along with the corresponding 90% exact binomial confidence interval. This similar methodology will be used to evaluate the proportion of agreement compared to histopathology and the rates of locoregional disease and suspected distant metastatic disease detected by ¹⁸F-fluciclovine-PET/CT. In addition, treating pathologic and/or biopsy findings as the reference standard, we will estimate the sensitivity and specificity of ¹⁸F-fluciclovine-PET/CT for detection of metastatic disease.

The analysis of the relationship of ¹⁸F-fluciclovine uptake on PET/CT (SUVmax) in primary bladder tumor to pathologic tumor grade/size after radical cystectomy will be analyzed using the Kruskal-Wallis test. The Wilcoxon-Rank-Sum test will be used to assess the association between SUVmax and the presence/absence of ASCT2 and LAT1 amino acid transporters in the resected primary bladder tumors.

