13.3 Sample Size, Accrual Rate and Study Duration

The planned sample size is 16 participants with completed ¹⁸F-fluciclovine-PET/CT scans and pathology dissection. Patients who did not complete the scans or without pathology dissection are unevaluable and will be replaced. Considering 4 patients who may be unevaluable and replaced, up to 20 patients can be enrolled. The estimated accrual rate is 1 participant/month, and accrual is expected to complete in another 16 months. Participants who undergo ¹⁸F-fluciclovine-PET/CT but have altered surgical plans due to clinical findings during surgery may remain evaluable and not replaced if a lymph node dissection was performed as determined by the study investigators. This will not affect the primary study objective given the primary objective is the agreement rate between PET/CT and pathology for metastases. Participants who do not undergo cystectomy will not be included for secondary objectives (2 and 3).

We will employ a Simon's 2-stage design to test the hypothesis that the agreement rate of metastatic disease status between ¹⁸F-fluciclovine-PET/CT and histopathology will be 75%, compared to a null agreement rate of 50%. In the first stage we will enroll 10 patients, and if 6 or more scans among those 10 are in agreement regarding metastatic disease status, we will open the second stage of accrual to enroll an additional 6 patients, making a total sample size of 16 patients. If fewer than 6 scans are in agreement in the first stage then the study may be stopped or the study design may be amended to enroll additional patients. In order to consider the study a success, a total of 11 or more scans need to be in agreement among all 16 scans. This design has a 0.62 probability of stopping early under the null, and has 79.9% power while maintaining an overall one-sided type I error rate of 0.101. The agreement rate between ¹⁸F-fluciclovine-PET/CT and histopathology is expected to be 75% (or higher) and the corresponding 90% CI will be (0.52, 0.91).

| Accrual Targets | | | |
|---|------------|--------|-------|
| Ethnic Category | Sex/Gender | | |
| | Females | Males | Total |
| Hispanic or Latino | + | = | = |
| Not Hispanic or Latino | + | = | = |
| Ethnic Category: Total of all subjects | (A1) + | (B1) = | (C1) |
| Racial Category | | | |
| American Indian or Alaskan Native | + | = | = |
| Asian | + | = | = |
| Black or African American | + | = | = |
| Native Hawaiian or other Pacific Islander | + | = | = |

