13.6 Analysis of Secondary Endpoints

Secondary objectives are to:

1. To determine the rate of detection of suspected distant metastatic disease by ¹⁸F-fluciclovine-PET/CT in patients with cT2-T4N0M0 muscle invasive bladder cancer by conventional CT/MRI imaging.

Endpoints:

- 1) Visualization and number of distant metastases on ¹⁸F-fluciclovine-PET/CT

Visualization of distant metastases on ¹⁸F-fluciclovine-PET/CT will be binary-categorized as present/absent. In the categorization, a qualitative scale (0-4) may be accounted and an optimal cut-off may be examined. We will compute sensitivity to compare ¹⁸F-fluciclovine-PET/CT with standard imaging modalities for distant metastases. The number of distant metastases will be descriptively shown by imaging modalities.

2. To correlate ¹⁸F-fluciclovine uptake on PET/CT in primary bladder tumor with pathologic primary tumor stage and size after radical cystectomy.

Endpoints:

- ¹⁸F-fluciclovine SUVmax in primary bladder tumor
- Primary tumor stage and size at radical cystectomy

The amount of ¹⁸F-fluciclovine accumulation in the primary bladder tumor on PET will be quantified using the maximum standardized uptake value (SUVmax). Tumor grade will be assessed histopathologically with specimens from cystectomy as part of standard-of-care. The correlations between ¹⁸F-fluciclovine uptake and tumor grade will be evaluated using Spearman correlation coefficients.

3. To correlate ¹⁸F-fluciclovine uptake on PET/CT to the presence/absence of ASCT2 and LAT1 amino acid transporters in the resected primary bladder tumors.

Endpoints:

- ¹⁸F-fluciclovine SUVmax in primary bladder tumor
- Presence/absence of ASCT2 and LAT1 amino acid transporter in resected primary bladder tumors

The Wilcoxon-Rank-Sum test will be used to assess the association between SUVmax and the presence/absence of a ASCT2 and LAT1 amino acid transporters in the resected primary bladder tumors.

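### Secondary objective 1: the sensitivity comparison for distant metastases cannot be interpreted in a cohort admitted as CT/MRI-negative, and the scan-only detection rate leaves out scanned patients without a dissection

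*Combined protocol and SAP*

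**What the plan says.** **Sensitivity.** For secondary objective 1, Section 13.6 commits to computing sensitivity to compare PET/CT "with standard imaging modalities for distant metastases". It names no reference standard there. Section 13.2 does: "treating pathologic and/or biopsy findings as the reference standard, we will estimate the sensitivity and specificity of" PET/CT for metastatic disease in general, and Section 13.1 counts both pelvic nodal and distant findings as a positive scan.

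**Entry.** Section 3.1.2 states: "Patients must have no definite evidence of locoregional or distant metastatic disease at the time of study eligibility", judged on conventional imaging. Footnote 1 of the study calendar (Section 10) makes that standard-of-care CT/MRI the comparator for PET/CT. No second CT/MRI is scheduled.

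**Follow-up.** The only after-study item in the calendar is the surgical specimen. Section 5.6 follows patients for at least 30 days but names no imaging or biopsy.

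**Analysis set.** Section 13.2 begins: "The primary and first secondary analyses will include all 16 eligible and treated patients with completed" scans and pathology dissection. Section 13.3 adds: "Patients who did not complete the scans or without pathology dissection are unevaluable and will be replaced". It also says: "Considering 4 patients who may be unevaluable and replaced, up to 20 patients can be enrolled". Patients whose operation changes because of what is found during surgery "may remain evaluable and not replaced if a lymph node dissection was performed as determined by the study investigators"; Section 5.3 agrees. Section 5.7 mentions replacement only for participants who leave before the PET/CT scan.

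**The concern.** A sensitivity comparison is informative only if both modalities had a chance to be positive and if cases missed by either can come to light. Here one modality was used to keep positive patients out, and disease that PET/CT misses at distant sites has no scheduled route to discovery. A published contrast could be read as evidence that PET/CT finds distant disease better than CT/MRI, when much of it was set by eligibility and by which lesions happened to be verified.

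The detection rate raises a different problem. Its endpoint, the presence and number of distant lesions on PET/CT, needs only a scan. Requiring a dissection discards usable scans from a very small sample. If the lack of a dissection is related to suspected spread, the exclusion also depends on the outcome.

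**Working it through.** **Interval method.** The plan gives no figure for this objective. Its 90% exact binomial interval has lower limit Beta(0.05; x, n-x+1) and upper limit Beta(0.95; x+1, n-x). For 12/16 this gives 0.516 to 0.910, matching the (0.52, 0.91) in Section 13.3.

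**1. CT/MRI sensitivity with pathology or biopsy as reference.** Sensitivity = true positives / patients with confirmed disease. Let k patients have confirmed distant disease. None had definite distant disease on CT/MRI, so CT/MRI scores 0/k unless an equivocal reading is counted as positive. If every confirmed case came from a PET finding, PET/CT scores k/k. The limits are 1 - 0.05^(1/k) and 0.05^(1/k).

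| k | CT/MRI 0/k, 90% upper limit | PET/CT k/k, 90% lower limit |
|---|---|---|
| 1 | 95.0% | 5.0% |
| 2 | 77.6% | 22.4% |
| 3 | 63.2% | 36.8% |

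**2. Effect of unseen PET misses.** The documents give no rate of distant disease, so this is purely illustrative. Assume 4 patients truly have it, PET/CT finds 2 (true sensitivity 50%), and both are biopsied in routine care.

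| PET-missed cases that surface | Observed PET/CT sensitivity (90% CI) |
|---|---|
| 0 | 2/2 = 100% (22.4-100%) |
| 1 | 2/3 = 66.7% (13.5-98.3%) |
| 2 | 2/4 = 50% (9.8-90.2%) |

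For the two biopsied cases, CT/MRI is 0/2 = 0% (0-77.6%) if neither was equivocal or if equivocal counts as negative. It rises to 2/2 if both were equivocal and counted as positive. The plan has no rule for scoring equivocal CT/MRI lesions.

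**3. Results that do not favour PET/CT.** If the only confirmed case is an equivocal CT/MRI lesion that PET/CT missed, and equivocal counts as positive, CT/MRI is 1/1 and PET/CT 0/1. If nothing is confirmed, both are 0/0.

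**4. CT/MRI read as the reference.** The denominator is the number of CT/MRI-positive patients. Eligibility makes this zero apart from equivocal readings, so PET sensitivity is 0/0 or rests on a handful of uncertain lesions.

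**5. Detection rate.** Let m of the 4 budgeted replacements have been scanned; the documents do not give m, so take 0 to 4. With x positive among the 16, the all-scanned rate lies between x/(16+m) and (x+m)/(16+m). For x = 1 (planned set 1/16 = 6.3%, 90% CI 0.3-26.4%):

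| m | Lowest (90% CI) | Highest (90% CI) |
|---|---|---|
| 0 | no change | no change |
| 2 | 1/18 = 5.6% (0.3-23.8%) | 3/18 = 16.7% (4.7-37.7%) |
| 4 | 1/20 = 5.0% (0.3-21.6%) | 5/20 = 25.0% (10.4-45.6%) |

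For x = 0, the planned 0/16 (0-17.1%) becomes, at m = 4, between 0/20 (0-13.9%) and 4/20 = 20% (7.1-40.1%). The highest values need every replaced patient who was scanned to be PET-positive at a distant site.

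**The case against.** - **It is a descriptive secondary objective in a 16-patient pilot.** No decision rule uses it, the rate is labelled as suspected disease, and counts by modality are already planned. This stands and limits the weight of the point. It does not rescue a sensitivity figure that eligibility largely determines.
- **Finding disease that CT/MRI missed is the purpose.** Agreed. The detection rate and the counts by modality serve that purpose without a sensitivity contrast.
- **A reader might infer that PET/CT must come out ahead whatever its true sensitivity.** The documents do not support that. Section 3.1.2 excludes only definite disease, so equivocal lesions can enter; Section 13.6 leaves the reference unstated; and step 3 shows a reversed result and an empty one. In step 2 the intervals also overlap widely.
- **A reader might infer that the detection rate is biased downward because PET findings cancel surgery.** No section says whether PET results reach the treating team or can change the operation. The altered surgery that Sections 5.3 and 13.3 describe arises from findings during surgery, and those patients may be kept: "the patient may remain evaluable if a lymph node dissection is performed as determined by the study team". The gap is confined to scanned patients with no dissection and may be empty.
- **The cut-off wording is only permissive.** True, and Section 5.4.2 labels scores 3 and 4 as probably and definitely malignant. No section makes that the formal threshold for the rate.

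**Conclusion.** The distant sensitivity comparison should not be reported as planned. With pathology or biopsy as reference, CT/MRI is at or near 0/k by selection and PET misses are not systematically ascertained, so the contrast is uninterpretable and likely, though not certain, to lean toward PET/CT. With CT/MRI as reference it is close to non-estimable. This follows from the eligibility rule and the schedule and does not depend on the four-case illustration.

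The analysis set for the detection rate is narrower than the endpoint requires. The effect ranges from none (m = 0) to outer bounds of 5.0% and 25.0% around an observed 6.3%; its direction is unknown. Neither part touches the agreement-rate design or its sample size.

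**What to change.** 1. **Section 13.6:** delete the sensitivity comparison for distant metastases and say that sensitivity is not estimated there. In its place, list PET-suspected distant lesions by site and score beside the CT/MRI reading of the same site, with confirmation status where routine-care results exist. Keep the planned counts by modality.
2. **Section 13.2:** limit the sensitivity and specificity estimates to locoregional (pelvic nodal) disease, where pathology is the reference. Otherwise 13.2 would still promise for distant sites what 13.6 has withdrawn.
3. **Section 13.2:** compute the secondary objective 1 detection rate in all eligible participants with a completed PET/CT (at most 20), with a 90% exact interval, and show the 16-patient result as a supplement. Reconcile the replacement wording of Sections 5.7 and 13.3.
4. **Section 13.6:** base the reported rate on a threshold on the 0-4 scale fixed before the analysis, and label any cut-off search exploratory.

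The cost is minor wording and the loss of a sensitivity figure that could not have been interpreted. No patients or procedures are added; routine biopsy results can come from the clinical databases in Section 12.1.1. One sentence should say until when they are collected, because Sections 5.1 and 5.5 end participation at surgery and set no such date for scanned patients who are never operated on.

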1.3 Secondary Objectives

1.3.1 To estimate the rate of detection of suspected distant metastatic disease by ¹⁸F-fluciclovine -PET/CT in patients with cT2-T4N0M0 muscle invasive bladder cancer by conventional CT/MRI imaging.

1.3.2 To investigate the relationship between ¹⁸F-fluciclovine uptake on PET/CT and pathologic tumor stage and size of primary bladder tumor after radical cystectomy.

1.3.3 To investigate the relationship between ¹⁸F-fluciclovine uptake on PET/CT and the presence/absence of a ASCT2 and LAT1 amino acid transporters in the resected primary bladder tumors.

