2. BACKGROUND

2.1 Urothelial carcinoma of the bladder

Urothelial carcinoma of the bladder is the fifth most common malignancy in the United States, with an estimated 75,000 new cases and 15,000 deaths in a year [1]. Approximately 25% of new cases are muscle-invasive bladder cancer (MIBC), while the rest are non-muscle-invasive bladder cancer (NMIBC). Accurate staging of bladder cancer is paramount in deciding the appropriate course of management. While NMIBC is generally managed by cystoscopic resection with intravesical BCG or chemotherapy, the standard treatment for MIBC is radical cystectomy (RC) preceded by neoadjuvant chemotherapy (NAC) in cisplatin-eligible patients [2-4]. It is estimated that ~30% of patients undergoing RC may have nodal metastases [5, 6]. Metastatic disease has exhibited improved outcomes when treated with first-line systemic cisplatin-based chemotherapy and salvage post-platinum therapy using one of multiple programmed death (PD)-1 and PD-ligand (L)-1 inhibitors (pembrolizumab, atezolizumab, durvalumab, nivolumab, avelumab) [7-13]. Additionally, pembrolizumab and atezolizumab are approved for the first-line therapy of cisplatin-ineligible patients based on durable responses [14, 15]. Therefore, pre-operative identification of those with node-positive metastatic disease will enhance prognostic risk stratification and tailoring of neoadjuvant therapy, for example with the consideration of clinical trials of more aggressive and promising neoadjuvant combination

regimens and tailoring the extent of lymph node dissection based on the extent of node-positive disease.

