5. IMAGING PLAN

5.1 Summary

All procedures will be performed on an outpatient basis. Expected toxicities and potential risks are described in Section 6 (Expected Toxicities and Dosing Delays/Dose Modification).

This is a pilot study investigating ¹⁸F-fluciclovine PET/CT for imaging patients with muscle invasive bladder cancer. The investigational imaging procedure in this study is ¹⁸F-fluciclovine-PET/CT.

After the participant meets eligibility criteria for the study and informed written consent is obtained, the participant will undergo the study procedure (¹⁸F-fluciclovine-PET/CT imaging). ¹⁸F-fluciclovine-PET/CT will be obtained within 6 weeks of the standard-of-care diagnostic staging procedures (MRI and/or diagnostic CT).

Participants will then undergo radical cystectomy per standard-of-care as determined by the medical oncologist. At the time of radical cystectomy, which usually includes pelvic lymph node dissection, standard evaluation of the surgical specimen will determine pathologic staging. We will assess the results of the standard evaluation of the surgical specimen for metastatic disease. These results will be compared with staging as determined by ¹⁸F-fluciclovine PET/CT and standard-of-care diagnostic imaging.

The participant will have completed all study requirements once tissue is obtained at radical cystectomy.

5.2 ¹⁸F-fluciclovine PET/CT imaging

5.2.1 The ¹⁸F-fluciclovine-PET/CT imaging procedure is described in Section 5.4.

Participants will be instructed to refrain from strenuous exercise for the 24 hours preceding the PET/CT exam, since amino acid transporters expression have been

noted to increase in skeletal muscle for that period after exercise [43]. Participants will be NPO for 4 hours prior to administration of ¹⁸F-fluciclovine.

5.2.2 Participants will be provided with instructions regarding what precautions to take at home once they receive the study agent. As with all radiopharmaceuticals administered, participants will receive a card stating that they have received a radiopharmaceutical for medical purposes which includes, but is not limited to, radiopharmaceutical, dosage, suggested time of detection, suggested contamination item storage duration, and institutional and departmental contact information.

Given the short half-life and diagnostic dose of ¹⁸F-fluciclovine (110 minutes), no special precautions regarding excreta or contact with other humans are necessary.

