13. STATISTICAL CONSIDERATIONS

13.1 Study Design, Objectives, and Endpoints

This is a prospective pilot study evaluating ¹⁸F-fluciclovine-PET/CT for detecting metastatic disease in patients with cT2-T4N0M0 muscle invasive bladder cancer.

The primary objective of this study is to estimate the agreement rate of metastatic disease status between ¹⁸F-fluciclovine-PET/CT and histopathology from radical cystectomy for detecting

locoregional metastatic disease in patients with cT2-T4N0M0 muscle invasive bladder cancer by conventional CT/MRI imaging. Secondary objectives include estimating of the rate of detection of suspected distant metastatic disease by ¹⁸F-fluciclovine-PET/CT, analysis of the association of ¹⁸F-fluciclovine uptake on PE/CT in primary bladder tumor with pathologic tumor grade/size after radical cystectomy, and analysis of ¹⁸F-fluciclovine uptake on PET/CT to the presence/absence of ASCT2 and LAT1 amino acid transporters in the resected primary bladder tumors.

The primary endpoints are metastatic disease status by ¹⁸F-fluciclovine-PET/CT and pathologic stage at radical cystectomy. The agreement rate is defined as the number of scans that are considered positive metastatic disease by both ¹⁸F-fluciclovine-PET/CT and histopathology and those considered negative metastatic disease by both ¹⁸F-fluciclovine-PET/CT and histopathology, out of all scans performed. A positive ¹⁸F-fluciclovine-PET/CT is defined as evidence of metastatic disease either regionally in the pelvic lymph nodes or distantly to bone, lungs, viscera, or lymph nodes outside of the pelvis. The ability of ¹⁸F-fluciclovine-PET/CT for detecting locoregional metastatic disease will be defined as the presence of disease detected locoregionally on ¹⁸F-fluciclovine-PET/CT. Secondary endpoints include visualization (present/absent) and number of distant metastases on ¹⁸F-fluciclovine-PET/CT. The amount of ¹⁸F-fluciclovine accumulation in the primary bladder tumor on PET will be quantified using the maximum standardized uptake value (SUVmax). Tumor grade/size and the presence of amino acid transporters will be assessed histopathologically with specimens from cystectomy as part of standard-of-care.

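### Secondary objective 2 names tumor stage and size, but the analysis text covers grade (with size only under a test whose groups are undefined), so the sections must be reconciled

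*Combined protocol and SAP*

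**What the plan says.** Section 1.3.2 sets uptake on PET/CT against "pathologic tumor stage and size of primary bladder tumor after radical cystectomy". Section 13.6 repeats stage and size in its objective line and lists as an endpoint "Primary tumor stage and size at radical cystectomy".

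The statistical text then changes variable. Section 13.1 restates the objective with grade and size and adds: "Tumor grade/size and the presence of amino acid transporters will be assessed histopathologically". Section 13.2 says that the relationship of SUVmax to "pathologic tumor grade/size after radical cystectomy will be analyzed using the Kruskal-Wallis test". Under objective 2, Section 13.6 names grade as the quantity read from the cystectomy specimen, and its only method sentence is that "uptake and tumor grade will be evaluated using Spearman correlation coefficients".

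Section 9 (Biomarker, Correlative, and Special Studies) says the correlation of imaging with surgical specimens follows Sections 2.5, 5.3 and 13.2. It does not cite 13.6.

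Two other places bear on the point. Section 5.1 states that "standard evaluation of the surgical specimen will determine pathologic staging", so stage will be available. Section 3.1.4 reads: "Patients may or may not have had prior neoadjuvant therapy prior to this study".

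**The concern.** Grade and stage are different pathology variables. An analyst who works from the method sentences would analyse grade, which neither Section 1.3.2 nor the 13.6 endpoint list mentions, and would leave out stage, which both name. For size, the analyst would have to invent groups before the one named test could be run, possibly after seeing the data. At stake is whether the results reported for objective 2 answer the question the protocol asks, and whether the size result depends on a choice the plan leaves open.

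**Working it through.** The plan states no numerical figure for objective 2, so the main check is a comparison of the text.

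**1. Variable and method, place by place**

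| Place | Pathology variable | Method named |
|---|---|---|
| 1.3.2, objective | stage, size | none |
| 13.1, objective restated | grade, size | none |
| 13.1, what pathology assesses | grade, size | none |
| 13.2, analysis | grade, size | Kruskal-Wallis |
| 13.6, objective line | stage, size | none (the verb is correlate) |
| 13.6, endpoint line | stage, size | none |
| 13.6, what pathology assesses | grade | none |
| 13.6, analysis | grade | Spearman |

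By variable:
- Stage: named in three objective or endpoint lines, with no method.
- Size: named in the same three lines, with one method (Kruskal-Wallis) and no groups.
- Grade: absent from those three lines, with two methods.

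**2. Is stage analysed elsewhere?** Stage also appears in 13.1 as part of the primary endpoint, in 13.2 in the cross-tabulation with PET metastatic status, and in 11.1 for comparison with image-based staging. None of these relates it to SUVmax.

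**3. Can Kruskal-Wallis be applied to size without groups?** No. The statistic is H = 12/(N(N+1)) × Σ(R_j²/n_j) − 3(N+1), where R_j is the rank sum of group j and n_j its size. Take N = 16 (the maximum under 13.2) and assume all sizes are distinct, so that each patient is a group of one. Then Σ(R_j²/n_j) = 1² + … + 16² = 16 × 17 × 33 / 6 = 1,496, and H = 12 × 1,496 / 272 − 51 = 66 − 51 = 15 = N − 1. H takes this value whatever the SUVmax data are, so size must be grouped first, and no section gives categories or cut-points. Spearman has no such requirement.

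**4. Which method governs?** Section 9 cites 13.2 only, and 13.2 is titled as the data analysis plan; both point to Kruskal-Wallis. Section 13.6, the section on secondary endpoints, names Spearman. The documents lean towards 13.2 but do not resolve the conflict.

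**5. Who enters the analysis?** Only those of the 16 who have cystectomy (13.2). Section 2.1 says that "the standard treatment for MIBC is radical cystectomy (RC) preceded by neoadjuvant chemotherapy (NAC) in cisplatin-eligible patients", and 3.1.4 admits pretreated patients, so a specimen without residual tumor is foreseeable. No section says how such a patient's stage and size enter. The documents give no frequency, so the effect cannot be quantified.

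**6. A wording slip nearby.** Section 5.4.2 defines a certainty scale from 0 to 4 but places regions of interest where the score is 3 to 5. Sections 13.1 and 13.6 quantify primary-tumor SUVmax with no score condition, so this is a minor correction.

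**7. Primary design, for completeness.** Continuing at 6 or more of 10 and succeeding at 11 or more of 16 gives an early-stopping probability of 0.623 and a one-sided error of 0.1012 at 50% agreement, and power of 0.79995 at 75%. These match the 0.62, 0.101 and 79.9% of Section 13.3 (the last by truncation). None of them uses tumor stage, size or grade against SUVmax.

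**The case against.** **Grade may simply be a slip for stage.** The 13.6 objective and endpoint lines say stage and size, and correlation coefficients follow directly. On that reading stage has two named methods and only a word is wrong. This is plausible and it stands as a possibility. A reader might infer that the stage half of objective 2 is bound to go unreported; the documents do not support that, because it follows only from the literal reading. Nor do they confirm a slip: grade is used consistently in 13.1, 13.2 and 13.6. Either way the text needs correcting, and only the sponsor can say which variable is meant.

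**The plan does give direction on method.** This stands in part. A reader might infer that nothing indicates which test governs, but Section 9 points to 13.2. It does not withdraw the Spearman sentence in 13.6.

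**Undefined size groups invite a false-positive figure.** A reader might try to put an inflated error rate on the free choice of size groups. That would need a significance level, a set of candidate groupings and a rule for picking the smallest p-value. The plan has none of these for objective 2, so such a figure would measure the assumptions and not the plan.

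**Kruskal-Wallis across stage categories is valid.** Agreed. Preferring Spearman for stage is a choice that uses the ordering; only for continuous size is its advantage clear.

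**The stakes are low.** Also agreed. Assuming a two-sided 5% level, which the plan does not set, and the approximation tanh(2.80 × √(1.06/(n − 3))), 80% power at n = 16 needs a correlation of about 0.66. Whatever is done, this objective can show only a strong association.

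**Conclusion.** The point holds as an internal inconsistency in secondary objective 2. The stage endpoint has no analysis if the text is followed literally, and a wording error must be corrected if grade was meant to read stage. Size has one named test, which cannot be run without groups that the plan does not define. Two methods are named, with a partial pointer to one of them.

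The effect is confined to secondary analyses in at most 16 patients. The primary endpoint, the two-stage rule and its error rates are unaffected. The conclusion rests on the wording alone and on no assumed effect size or error level. The coding of patients without residual tumor and the score range in 5.4.2 are minor additions that do not carry the point.

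**What to change.** Before SUVmax and pathology are analysed together:

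- The sponsor confirms that stage is the intended variable, as 1.3.2 and the 13.6 objective and endpoint lines state, and makes 13.1, 13.2 and 13.6 match.
- Analyse SUVmax against size as a continuous variable and against ordered pT stage, both with Spearman, which 13.6 already names and which needs no cut-points. State that this analysis governs.
- Keep Kruskal-Wallis across pT categories as a supporting analysis if wanted, and label any grade analysis descriptive.
- Add 13.6 to the cross-reference in Section 9.
- State how patients with no residual tumor enter the stage and size analyses. One workable convention is lowest stage category and size zero, with a repeat analysis leaving them out.
- In 5.4.2, make the score range for regions of interest fit the 0 to 4 scale.

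The cost is wording in five sections (5.4.2, 9, 13.1, 13.2 and 13.6). No patients, procedures or measurements are added: stage comes from the standard specimen evaluation in 5.1 and size from the standard-of-care histopathology in 13.1.
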